**STUDY SUMMARY:**

Investigational Agent(s) (Drugs or Devices)	Biostim-5 Spinal Stimulator
IND / IDE / HDE #	NSR
Indicate Special Population(s)	 Children  Children who are wards of the state  Adults Unable to Consent  Cognitively Impaired Adults  Neonates of Uncertain Viability  Pregnant Women  Prisoners (or other detained/paroled individuals)  Students/Employees
Sample Size	36 (up to 75 screened)
Funding Source	Max Nader Center, Craig H. Nielsen Foundation, and the Shirley Ryan AbilityLab Catalyst Grant Program
Indicate the type of consent to be obtained	 Written  Verbal/Waiver of Documentation of Informed Consent  Waiver of HIPAA Authorization   Waiver/Alteration of Consent Process
Site	 Lead Site (For A Multiple Site Research Study)  Data Coordinating Center (DCC)
Research Related Radiation Exposure	 Yes  No
DSMB / DMC / IDMC	 Yes  No

**OBJECTIVES:**

- To determine whether acute intermittent hypoxia therapy (AIH) combined with transcutaneous electrical spinal cord stimulation during ambulation training modulates spinal locomotor networks in individuals with spinal cord injury

- To determine whether acute intermittent hypoxia therapy (AIH) combined with transcutaneous spinal cord stimulation during ambulation training improves locomotor function in individuals with spinal cord injury
- To determine whether ambulation efficiency (improved cardiovascular conditioning) improves with training combination of AIH, transcutaneous spinal cord stimulation and ambulation training in individuals with spinal cord injury

## **STUDY ENDPOINTS:**

Primary endpoints:

- Change in locomotion efficiency as measured by the 6-Minute Walk West (6MWT)

Secondary endpoints

- Change in Ten Meter Walk Test (10MWT) at self-selected velocity and fastest (safe) velocity
- Change in maximum volitional isokinetic and isometric ankle and knee torque as measured by the Biodex dynamometer strength assessment
- Change in transfers
- Change in bilateral lower extremity strength

## **STUDY INTERVENTION(S) / INVESTIGATIONAL AGENT(S):**

**Transcutaneous Spinal Cord Stimulation:** A Transcutaneous Spinal Cord Neurostimulator (BioStim-5 or NeuroEnabling Stimulator System) will deliver transcutaneous electrical spinal cord stimulation. It provides constant current stimulation with a range of 0-250 mA through self-adhesive electrodes (ValuTrode, Axelgaard Ltd., USA) with a diameter of 3.2 cm placed as cathodes on the skin between the spinous processes of the vertebrae. In addition, two 7.5 × 13 cm self-adhesive electrodes serving as anodes (ValuTrode, Axelgaard Ltd., USA) will be placed symmetrically on the skin over the iliac crests. A foam rubber pad will be placed over the cathodes and secured using adhesive tape, and an elastic belt will be wrapped tightly around the trunk above the waist to ensure a constant pressure between the electrodes and the skin. The stimulation waveform will consist of monophasic or biphasic, rectangular 1-ms pulses at a frequency ranged between 0.2 and 40 Hz, with each pulse filled with a carrier frequency of 5 to 10 kHz. The stimulation intensity will vary from 10 to 250 mA and be determined based on participant threshold and maximum motor outputs.

**Acute Intermittent Hypoxia (AIH):** Intermittent hypoxia will be administered within a clinical research laboratory. Subjects will be fitted with a latex-free full non-rebreather mask with a custom neoprene head strap [Hypoxico Inc., New York, NY, USA]. This mask and oxygen delivery system are commonly used for altitude training. The mask will first provide a normoxic air (room air) mixture ( $\text{FiO}_2 = 0.21$ ) via the mask. The mask is designed to couple with a universal mask circuit connecting to the air mixture system. The purpose of the mask will be to minimize room air entrainment. The non-rebreather mask has an attached reservoir bag where the controlled air mixture ( $\text{FiO}_2 = 0.08 - 0.95$ ) from the generator fills in between breaths, and a valve that largely prevents the inhalation of room or exhaled air. Delivery of air mixtures will be done through adjustment of one-way valves attached to the delivery cylinders. Tubing will extend from the reservoir bag directly to the machine.

Once fitted with the mask, initial recordings of heart rate, blood pressure, and arterial oxygen saturation ( $\text{SpO}_2$ ) will be taken. The sequence of hypoxia will consist of up to 60- 90 seconds of 9-10%  $\text{O}_2$  ( $\text{FiO}_2 0.09$ ), alternating with up to 60- 90 seconds of 21%  $\text{O}_2$  (normoxic air  $\text{FiO}_2 0.21$ ). The delivery of hypoxia and normoxic air mixtures will be repeated up to 18 times per session

each, for a total of up to 45 minutes, to maintain SpO2 at 80-90%. Heart rate and pulse oximetry will be continuously monitored throughout, and recording will be taken at each alteration in sequence. Blood pressure will be taken upon completion of the total sequence.

A pulse oximetry unit will provide continuous monitoring of heart rate and peripheral arterial oxyhemoglobin saturation (SpO2). SpO2 will be maintained at a goal of 80-90% during the hypoxic bouts, however, SpO2 as low as 75% will be accepted. If the SpO2 drops below 75%, we will terminate the hypoxia exposure immediately.

Any subjective symptoms will be recorded and the subject will be monitored throughout the study period for any signs of cardiopulmonary distress.

If there is a dangerous alteration in the cardiopulmonary parameters being assessed, the experiment will be stopped and appropriate care will be provided by the resident on call or nursing staff available at the Shirley Ryan AbilityLab.

All research devices will remain at the Shirley Ryan AbilityLab in a secure research location. Only authorized research personnel will have access to the devices.

All research procedures will be performed at the Shirley Ryan AbilityLab (SRALab) in the Research & Technologies Lab (RT&O).

### **PROCEDURES INVOLVED:**

Study Design: A randomized, controlled crossover trial. We are evaluating the effectiveness of AIH prior to transcutaneous spinal cord stimulation during locomotor training on improving ambulation and standing balance among individuals with paraplegia or tetraplegia due to spinal cord injury. All participants will complete three arms of the study:

1. AIH prior to transcutaneous spinal cord stimulation during locomotor training (AIH + tSCS)
2. Sham AIH prior to sham transcutaneous spinal cord stimulation during locomotor training (SHAM + SHAM)
3. Sham AIH prior to transcutaneous spinal cord stimulation during locomotor training (SHAM AIH + tSCS)

Participants will complete a 4-week washout period between each arm.

Prior to Visit 2, a medical clearance letter describing study procedures and risks will be sent to the subject's physician or clinician to request medical clearance for the subject to participate in the study. Permission to contact the participant's physician or clinician to obtain medical clearance will be obtained during the screening process.

### **Visit 1: Initial screening session**

- Obtain voluntary and informed consent
- Obtain medical clearance from subject's physician
- Inclusion/exclusion criteria checklist reviewed with patient
- Medical history review
  - Patient name
  - Patient date of birth
  - Patient race (voluntary)
  - Patient gender
  - Emergency contact information

- Date of spinal cord injury
- Type and location of spinal cord injury
- AIS level
- Assistive device use
- Orthotic use
- Recent surgery/injuries
- Medications
- Allergies
- Medical History
- Therapy history
- Physical Function Assessment
  - Skin assessment
  - Active and passive range of motion (AROM/PROM) of bilateral lower extremities
  - Assessment of lower extremity spasticity using Modified Ashworth Scale
  - Manual muscle testing of bilateral lower extremities as an assessment of strength
  - Ten Meter Walk Test (10 MWT): Assesses subject walking speed in meters per second for 10 meters. Subjects will repeat each measure 3 times at their normal self-selected walking speed and 3 times at a fast speed while still able to maintain safety. The test may then be repeated without lower extremity orthotics and without assistive devices for a total of up to 18 trials.

**Baseline Assessments:**

- Standard evaluation of physical function
  - Active and passive range of motion of bilateral lower extremities
  - Assessment of lower extremity spasticity using Modified Ashworth Scale
  - Skin integrity screen
- Assessment of maximum isometric voluntary ankle torque generation: Subjects will be instructed to contract, and for continued voluntary torque production will be encouraged using verbal commands for a period of approximately 5 seconds. The hip will be flexed up to 90-100°, the knee flexed up to 10° and the ankle at 0° plantar flexion, as described in previous studies (Shaffer, Okereke et al. 2000; Pathare, Walter et al. 2005). Axis of ankle rotation will be aligned with the axis of rotation of the dynamometer. The foot will remain secured to a footplate with straps placed at the forefoot and ankle. The knee will be braced to eliminate moments generated by hip adduction/abduction. Subjects will exert constant endpoint forces against the dynamometer with the weight of the limb supported by the device.
- Timed Up and Go Test (TUG): Assesses mobility, balance, walking ability and fall risk. The participant starts seated in a chair with his/her back against the chair back. On command, the participant rises from the chair, walks 3 meters, turns, walks back to the chair and sits down. Timing begins when the command to start is given and stops when the participant returns to a seated position. This test may be repeated up to 3 times during each assessment visit and during each training visit.
- Six Minute Walk Test (6 MWT): The 6MWT is performed as an objective evaluation of functional exercise capacity. The 6MWT is easy to administer, well tolerated, and typically reflective of activities of daily living. The test measures the distance that the patient can walk on a flat, hard surface, indoors, in a period of 6 minutes. The walk test is self-paced and assesses the level of functional capacity. Patients are allowed to stop and rest during the test, however, the timer does not stop. If the patient is unable to

complete the time, the time stopped is noted and reason for stopping prematurely is recorded.

- Ten Meter Walk Test (10 MWT): Assesses subject walking speed in meters per second for 10 meters. Subjects will repeat each measure 3 times at their normal self-selected walking speed and 3 times at a fast speed while still able to maintain safety.
- Spinal Motor Evoked Potentials (MEPs) may be obtained at baseline and during all functional assessment visits while stimulating interspinous spaces with single pulses at each stimulation intensity. MEPs are the electromyographic responses of the peripheral muscles to electrical stimulation of the spinal cord. MEPs will be used to test the integrity of the motor pathways of the spinal cord.

### **Treatment Sessions**

Each participant will complete 5 treatment sessions in each of the 3 arms of the study. Treatment sessions will take place 5 times per week.

Each treatment session may include:

- *Arm 1: AIH + tSCS*
  - May receive up to 45 minutes of AIH and 30 min of locomotion training with transcutaneous spinal cord stimulation.
- *Arm 2: SHAM + SHAM*
  - May receive up to 45 minutes of sham AIH and 30 min of locomotion training with sham transcutaneous spinal cord stimulation.
- *Arm 3: SHAM AIH + tSCS*
  - May receive up to 45 minutes of sham AIH and 30 min of locomotion training with transcutaneous spinal cord stimulation.

Under all of the conditions, the goal during locomotor training is to generate smooth and symmetrical stepping movements. The trained research personnel will provide cues (verbal, visual and tactile) to improve symmetry of gait and avoid compensatory mechanisms. The progression in training refers to gradually increasing gait speed while maintaining improved gait kinematics. Electromyographic (EMG) activity will be collected from the lower extremity muscles bilaterally during maximum voluntary contractions and locomotor training.

### **Functional Assessment Visits**

Occur after completion of each arm

- Refer to Baseline Assessment Visits for repeat of assessments

All visits will be conducted under the supervision of a trained researcher and clinician. Manual assistance or cueing will be provided as necessary for safety and balance. Clinicians will also utilize gait belts and overhead harness systems to ensure patient safety during physical activity. Vital signs will be monitored with use of our wearable sensors before, during and after physical exertion. All subjects will be permitted to stop physical activity or rest at any time during the study. In addition, the following patient reports will be used to assess patient participation and make adjustments as appropriate.

- Rating of Perceived Exertion (RPE): The 15-grade Borg Scale during ambulation training (over ground, treadmill and gravity-eliminated) to monitor RPE. The intensity will be adjusted to ensure patients do not exceed a rating of 17 (very hard).
- Pain scale: Visual Analogue Scale (VAS) for pain will monitor patient discomfort during non-invasive spinal cord stimulation and locomotion training parameters. This is a 10-

point scale. We will stop when the participant states pain that interferes with their safe participation in the research.

Finally, any adverse reactions that result from participation in this study will be documented by the principal investigator on the subject's data file and reported in writing to Northwestern's Office for Protection of Human Subjects.

Video recording and/or pictures of each participant during assessments may be taken during the training and testing sessions. These items may be used to help troubleshoot potential issues. They may also be used for presentations and training of other research personnel. All attempts will be made to ensure the images or videos used are devoid of any identifying information. Each subject may choose to limit if/how these items may be used, as indicated during their consent process.

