## **INCLUSION AND EXCLUSION CRITERIA**

### **Inclusion Criteria:**

- Participants have been diagnosed with a spinal cord injury below level C2
- ASIA Impairment Scale Grade A-D
- Participants are 18 years of age or older
- Participants are at least 6 months post spinal cord injury
- Participants with paraplegia or tetraplegia secondary to a single spinal cord injury
- Participants are able to provide informed consent
- Participants are not currently receiving regular physical therapy services

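### Reported pain is the only monitor and stop trigger that names spinal stimulation; participants who may lack feeling at the electrode sites are eligible, and no skin check is scheduled at the 15 treatment visits

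*Combined protocol and SAP*

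**What the plan says.** **Monitoring.** Functional Assessment Visits introduces two self-report scales by saying that "the following patient reports will be used to assess patient participation and make adjustments as appropriate". One is the Borg exertion rating. The other is the only monitor in the supplied text that mentions spinal stimulation: "Visual Analogue Scale (VAS) for pain will monitor patient discomfort during non-invasive spinal cord stimulation and locomotion training parameters". Its stop rule is "We will stop when the participant states pain that interferes with their safe participation in the research".

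**Who is eligible.** Inclusion Criteria lists "ASIA Impairment Scale Grade A-D" and "Participants have been diagnosed with a spinal cord injury below level C2". Neither the inclusion nor the exclusion list asks for sensation at the electrode sites or for walking ability. Active pressure sores are an exclusion, so the protocol already treats skin as a hazard.

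**What touches the skin.** Under Study Intervention(s), the small electrodes are "placed as cathodes on the skin between the spinous processes of the vertebrae", with no vertebral level given. Two large anodes go over the iliac crests. A foam pad and tape cover the cathodes, and "an elastic belt will be wrapped tightly around the trunk above the waist to ensure a constant pressure between the electrodes and the skin". Current ranges from 10 to 250 mA and is set from threshold and motor output.

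**When skin is examined.** There is a skin assessment at Visit 1. Baseline Assessments lists "Skin integrity screen", and the functional assessment visits repeat the baseline list by cross-reference. Treatment Sessions lists no skin check in any arm.

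**The concern.** A safeguard that relies on the participant feeling pain needs intact sensation under the electrodes and belt. The trial admits complete injuries, and nothing in its criteria ensures that sensation. Where the injury lies above the electrode dermatomes, the participant may feel little or nothing there, and the stop rule followed as written could then give no signal while skin is being harmed. Participants graded B to D may also have reduced feeling.

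An observed skin finding does not depend on sensation, and the protocol already has such a check. It is scheduled before and after each block of five sessions but not within the block, when electrodes, belt and current are applied. A problem that began after the first session of an arm would meet no scheduled check until POST.

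What is at stake is participant safety and the ability to link a skin event to a session. No endpoint, comparison or power figure is affected.

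**Working it through.** The plan states no figure on this point to reproduce. The check sets the sections side by side and counts visits.

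**1. Safeguards in the supplied text**

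| Safeguard | Section | Names stimulation? | Independent of sensation at the electrodes? |
|---|---|---|---|
| Pain scale and stated-pain stop | Functional Assessment Visits | Yes, together with locomotion training | No |
| Borg exertion rating | Functional Assessment Visits | No | Yes, but measures effort |
| Vital signs by wearable sensor | Functional Assessment Visits | No | Yes, but does not show skin injury |
| Clinician supervision | Functional Assessment Visits | No | Yes, but schedules no skin check |
| Saturation and cardiopulmonary stops | Study Intervention(s), hypoxia text | No | Yes, but concern hypoxia |

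The 10 to 250 mA rule says how intensity is set; it is not a safety stop.

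**2. Scheduled skin checks per participant** (visit counts from Study Timelines)

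- Screening 1 + baseline 3 + POST 3 + 1 week 3 = 10.
- Treatment visits: 3 arms × 5 sessions = 15, with 0 scheduled checks.

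**3. Exposure per participant** (from Treatment Sessions)

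- Per arm: 5 sessions × 30 min = 150 min between that arm's baseline and POST checks.
- Two arms give active stimulation: 2 × 5 = 10 sessions, and 10 × 30 min = 300 min.
- Within each arm, sessions 2 to 5 are reapplications with no scheduled check since the previous session: 4 per arm, so 2 × 4 = 8 per participant.

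**4. Range over the trial**

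Let k be the number of participants with insensate electrode skin. The documents do not give k, so it runs from 0 to the planned 36.

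- Reapplications without a scheduled check among them = 8 × k.
- k = 0 gives 0; k = 1 gives 8; k = 36 gives 8 × 36 = 288.
- The Statistical Analysis Plan names an INT5 time point, but Study Timelines lists no INT5 assessment visit. If INT5 did include a skin check before session 5, the count per arm falls to 3, and the ceiling to 2 × 3 × 36 = 216.
- The sham-stimulation arm would add at most 4 × 36 = 144 belt and electrode reapplications, without active current. This assumes that both are worn there, which the text does not state.

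These are counts of opportunities for a check. The documents give no rate of skin injury with this device, so no expected number of events can be derived.

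**The case against.** **A clinician is present at every visit and handles the sites.** This stands in part. Electrodes are placed on the skin, padded, taped and belted, so staff may well see a problem, and adverse reactions must be documented on the participant's file. A reader might infer that skin is never looked at between sessions, that an injury would surface only at POST, or that it could not be traced to a session. The documents support none of these; they show only that no check is scheduled.

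**Loss of feeling is not certain.** This stands. A reader might infer that the pain trigger cannot work in any AIS A participant. Whether it can depends on injury level relative to electrode site, and the cathode levels are not given.

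**The number affected may be small or zero.** This stands. The trial is built on walking tests, and few participants with complete injuries may be able to do them. No criterion excludes them, however. The figure of 288 would be misread as a count of unsafe applications or expected injuries.

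**The current is pulsed and individually set.** True: 1-ms pulses with a 5 to 10 kHz carrier, with intensity set from threshold and motor output. This may limit risk, but it does not replace a check for harm, and the documents quantify neither.

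**The supplied text is incomplete.** No risk section is included, and one could address skin. The point is limited to what is shown. Treatment Sessions, where a per-session check would be expected, is present and lists none.

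**The sections do not contradict one another in words.** Correct. The misfit lies between a monitor that assumes sensation and criteria that do not require it. That calls for reconciliation by the sponsor and does not call for a clinical rule from this review.

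**Conclusion.** The point holds in limited form. Reported pain is the only monitor and stop trigger that names spinal stimulation, although it also covers locomotion training. It may stay silent in eligible participants whose injury lies above the electrode dermatomes. The protocol's own skin screen brackets each five-session block but is not scheduled inside it: 10 scheduled checks per participant, none at the 15 treatment visits, against 300 minutes of active stimulation.

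The size of the affected group is unknown, so 0 to 288 reapplications is a range of missed scheduled checks and not an estimate of harm. The conclusion rests on the supplied text being complete for treatment-session procedures and on some participants having insensate skin at the electrode sites. The change is worth making because it improves safety at little cost.

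**What to change.** 1. In Treatment Sessions, schedule the skin integrity screen already listed under Baseline Assessments at each treatment session in all three arms, with the finding recorded by session. At one screen per session, scheduled checks rise from 10 to 10 + 15 = 25 per participant.
2. Reconcile the pain-based stop text under Functional Assessment Visits with the electrode and belt description under Study Intervention(s) and with Inclusion Criteria, for participants without sensation at the electrode sites. The sponsor decides how; no stopping criterion is proposed here.

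**Cost.** The clinician already present can do the screen. A few minutes per session is an assumption, as the documents give no time. Sessions become slightly longer and the session form gains one line. No visit and no change to the analysis are needed.

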## **STUDY TIMELINES**

- One (1) screening visit
- One (1) Baseline assessment visit prior to initiating each arm (3 total)
- Fifteen (15) treatment/intervention visits, 5 per each intervention arms
  - The treatment sessions will be up to 5 times per week within each participants' scheduling availability
- One (1) Functional Assessment visit that occurs after all intervention sessions are complete for each arm (POST, 3 total)
- One (1) Functional Assessment visit that occurs 1 week after all intervention sessions are complete for each arm (1 week follow up, 3 total)

We anticipate an ongoing enrollment over 3 years. Investigators will complete this study (primary analyses) 5 years from start date (IRB approval date).

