#### STATISTICAL ANALYSIS PLAN:

All functional gait outcomes will be assessed at three follow-up visits. We will use a linear mixed model with repeated measures to jointly assess changes at INT5, POST and 1WK relative to baseline within each arm as well as assess the changes between arms for each time point. The model will include time points (BL, INT5, POST, and 1WK as a categorical variable) and treatment arm (AIH + tSCS, SHAM AIH + tSCS, and SHAM + SHAM as categorical variable) as fixed effects and subject as a random effect. Linear mixed models provide a better mechanism for handling missing data by using all available data, rather than performing a complete case

analysis, if the data are assumed to be missing at random. The level of significance will be set at alpha = 0.05. Bonferroni corrections will be used to adjust for multiple comparisons.

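### The sole adverse-event rule makes causality a condition of recording, so events judged unrelated need not be logged and any later summary of harms by arm would be incomplete

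*Combined protocol and SAP*

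**What the plan says.** The adverse-event rule stands near the end of Functional Assessment Visits: "any adverse reactions that result from participation in this study will be documented by the principal investigator". The same sentence goes on to require written reporting to the university's Office for Protection of Human Subjects. The text supplied contains no definition of an adverse event, no procedure for assessing causality, and no requirement to log events whatever their cause.

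Some information is collected without a causality test:

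- The AIH part of Study Intervention(s) says: "Any subjective symptoms will be recorded and the subject will be monitored throughout the study period for any signs of cardiopulmonary distress". It also says: "Heart rate and pulse oximetry will be continuously monitored throughout, and recording will be taken at each alteration in sequence".
- Functional Assessment Visits adds exertion ratings, vital signs around exertion, and a pain scale: "Visual Analogue Scale (VAS) for pain will monitor patient discomfort during non-invasive spinal cord stimulation and locomotion training parameters".
- A skin screen and the Modified Ashworth Scale are among the Baseline Assessments and are repeated at the functional assessment visits.

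The design has sham arms, including "Sham AIH prior to sham transcutaneous spinal cord stimulation during locomotor training (SHAM + SHAM". Objectives and Study Endpoints name no safety item. The Statistical Analysis Plan is confined to function: "All functional gait outcomes will be assessed at three follow-up visits". Study Summary records that there is no data monitoring board.

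**The concern.** As worded, the rule filters on causality before anything is written down. A fall at home or a urinary tract infection judged unrelated need leave no trace. If such events later proved to cluster in one arm, nobody could go back and reconsider, because there would be no list to reconsider. With no monitoring board, no outside body is placed to ask.

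The plan itself treats such events as relevant: Exclusion Criteria bars people with active urinary tract infection, unhealed fractures or painful musculoskeletal dysfunction. If one of these arises during the study and is judged unrelated, the plan requires no record of it, although it might explain a missed session or a poor walk test.

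Every participant passes through real and sham conditions, so a descriptive count of harms by arm would be informative at little cost. The current rule would not supply complete data for one.

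**Working it through.** The plan gives no figure on this point, so there is none to reproduce. The check is in two parts: what the text captures, and what a causality filter can do to a count.

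**1. What is captured whatever the cause**

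| Source in the plan | What it captures | Medical event between visits? |
|---|---|---|
| AIH procedure | Symptoms, heart rate, oxygen saturation | No; written as part of the AIH procedure |
| Functional Assessment Visits | Pain, exertion, vital signs | No; tied to sessions, and the ratings serve to judge participation and make adjustments |
| Baseline Assessments, repeated after each arm | Skin integrity, spasticity | Only a skin or spasticity change still present at the visit |
| Adverse-event sentence | Reactions resulting from participation | Only if judged to result from participation |

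From Study Timelines, the skin and spasticity checks fall at 3 baseline + 3 POST + 3 one-week visits = 9 scheduled points per participant, at the same points in every arm. They therefore give reasonable cover for skin and spasticity. A fall at home or a urinary tract infection appears in no row unless it passes the causality test.

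**2. What the filter can do**

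Recorded risk = true risk × probability that an event is attributed to participation. The documents give neither quantity, so every input below is an assumption, chosen to show a range.

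| True risk, real v sham | Attribution, real v sham | Recorded risk, real v sham | Recorded difference | True difference |
|---|---|---|---|---|
| 20% v 20% | 60% v 60% | 12% v 12% | 0 points | 0 points |
| 20% v 20% | 50% v 40% | 10% v 8% | +2 points | 0 points |
| 20% v 20% | 80% v 40% | 16% v 8% | +8 points | 0 points |
| 20% v 20% | 40% v 80% | 8% v 16% | −8 points | 0 points |
| 30% v 15% | 60% v 60% | 18% v 9% | +9 points | +15 points |
| 30% v 15% | 40% v 80% | 12% v 12% | 0 points | +15 points |

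In the third row, with the planned 36 participants in each condition, the file would show 36 × 0.16 = 5.8 against 36 × 0.08 = 2.9 participants with an event, where the true number is 36 × 0.20 = 7.2 in each.

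Two things follow. Equal attribution creates no false difference between arms, though it loses events and shrinks a true difference (15 points to 9). A false difference needs attribution that differs by arm, and its sign depends on which arm's events are attributed more readily.

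**The case against.** The strongest reply is that the sentence couples documenting with reporting, so it can be read as the duty to report related events; it does not forbid recording others. It names the principal investigator as the person who documents, and does not say who judges causality. Both points are fair. Still, no other sentence requires unrelated events to be recorded, so a site that follows the text exactly need not record them.

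Four stronger readings are tempting, and the documents do not support them.

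- A reader might infer that unrelated events leave no record of any kind. The symptom, pain, vital-sign, skin and spasticity checks contradict that.
- A reader might infer that a planned safety comparison is biased. None is planned, so the point concerns any summary made later.
- A reader might infer that events under real hypoxia will be attributed more readily. That is plausible: staff who see the saturation readings at each alternation could guess the arm, and the documents do not say that the person documenting events is blinded. It is not shown, and the opposite tendency is possible.
- A reader might infer that unequal observation time biases the arms. The plan says "Participants will complete a 4-week washout period between each arm", so after the first two periods a further baseline follows about 4 weeks later, whereas after the third the last scheduled contact is at 1 week. This difference is by period, not by arm. It would largely cancel with balanced sequences; the sequence scheme is not described, so imbalance is possible but not demonstrated.

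**Conclusion.** The concern holds in a limited form. The sole adverse-event rule makes causality a condition of entry, and the other checks do not capture medical events between visits. Any later summary of harms by arm would be incomplete, and it could be biased in either direction if attribution differed by arm. That conclusion about completeness rests on the wording alone.

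The size of any bias cannot be estimated from the documents. Under the assumed inputs it runs from none (equal attribution, equal risk), through 2 points, to 8 points either way, and in one case a true doubling from 15% to 30% disappears. These figures show what is possible, not what is expected. No planned efficacy analysis or sample-size figure is affected. The change is worth making because it is cheap and because unrecorded events cannot be reliably recovered afterwards. Nothing here is inferred from the pages removed before review.

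**What to change.** Replace the adverse-event sentence under Functional Assessment Visits with a rule on these lines:

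- Ask about and record all adverse events, related or not, at every treatment, baseline and follow-up visit, with onset date, arm and period. From Study Timelines that is 15 treatment + 3 baseline + 6 functional assessment visits = 24 existing contacts, so no visit is added.
- Assess relatedness afterwards in a separate field, blind to arm where feasible. Relatedness continues to govern reporting to the Office for Protection of Human Subjects.
- Add to the Statistical Analysis Plan a descriptive table of events by arm, over the same window in each period. The window runs from the first session to the visit described as "One (1) Functional Assessment visit that occurs 1 week after all intervention sessions are complete for each arm". List later washout events separately.

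The cost is protocol wording, a standard question and a relatedness field on existing forms, and a short table. The downside is more unrelated events to record in a population where complications may be common. The external reporting burden does not change.
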